10.6 Safety Analyses

10.6.1 Adverse Events

The Medical Dictionary for Regulatory Activities (MedDRA) version 20.1 or later will be used to code all events categorized as adverse events (AEs) to a system organ class and a preferred term. Severity of AEs will be graded using the CTCAE (Appendix B) and recorded on the eCRF. All adverse event tables will be summarized by actual treatment group. Treatment-emergent adverse events are events with an onset after the administration of the first dose of IP.

Subject Incidence of AEs will be summarized for all treatment-emergent AEs, serious AEs, adverse device effects (ADEs; i.e. device-related adverse events), AEs leading to withdrawal of investigational product and fatal AEs. Subject incidence of all treatment-emergent AEs, serious AEs, AEs leading to withdrawal of investigational product, and fatal AEs will be tabulated by system organ class and preferred term.

Summaries of treatment-emergent AEs occurring in at least 1% of the subjects by preferred term in any treatment arm will be provided in descending order of frequency.

Subject incidence of adverse events related to a device will be tabulated by preferred term in descending order of frequency by treatment group.

A separate summary of any adverse events collected during the lipid stabilization period will be provided for all subjects in the LSAS.

Subject incidence of adverse events associated with lipid lowering therapies:

- Muscle-related
- Liver-related

associated with injectable protein therapies:

- Injection site reactions
- Hypersensitivity or allergic reactions

potential hepatitis C infections and potential neurocognitive events will be summarized by category and preferred term.

10.6.2 Laboratory Test Results

Descriptive statistics will be provided for actual values and changes from baseline in select laboratory parameters at each protocol-specified scheduled visit. Laboratory analytes are provided in the protocol Table 2. Lab shift tables using the CTCAE v4.03 or later grading will be used for select analytes of interest, when applicable. The results will

be based on the maximum (i.e., worst) shift from baseline to the EOS. In addition, CK and liver function test (LFT) abnormalities will be assessed by the incidence overall and by visits of the following categories:

- CK > 5 x ULN
- CK > 10 x ULN
- ALT or AST > 3 x ULN
- ALT or AST > 5 x ULN
- Total Bilirubin > 2 x ULN
- (ALT or AST > 3 x ULN) and Total Bilirubin > 2 x ULN and Alkaline Phosphatase < 2 x ULN

10.6.3 Vital Signs

Systolic and diastolic blood pressure and heart rate will be summarized for each treatment group using descriptive statistics at each scheduled visit.

10.6.4 Electrocardiogram (ECG)

For post-baseline assessments where ECG is performed in triplicate, the average of the 3 (or all available) readings will be used for analysis. Observations with the following diagnosis or findings will be excluded from analysis: artificial pacemaker, atrial fibrillation, atrial flutter, left bundle branch block, and right bundle branch block.

PR, QRS, QT, QTc (i.e., QTcB and QTcF) and RR intervals and their change from baseline will be summarized for each treatment group by scheduled visit. In each treatment group, subjects will be categorized and summarized per their maximum post-baseline absolute QTc interval using limits of 450 ms, 480 ms, and 500 ms. They will also be categorized per their maximum change from baseline QTc interval using limits of 30 ms and 60 ms.

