10.5.3 Safety Endpoints

Adverse Events

Adverse events will be coded using the current version of the Medical Dictionary for Regulatory Activities (MedDRA). Subject incidences of treatment-emergent adverse events, serious adverse events and adverse events leading to discontinuation of IP will be tabulated by system organ class and preferred term for each treatment group.

Safety Laboratory Parameters

Laboratory parameters will be summarized for each treatment group using descriptive statistics at each scheduled assessment. Laboratory shift tables for certain analytes will be provided using the CTCAE v.4 toxicity criteria. The results will be based on the maximum (ie, worst) shift from baseline to the EOS.

Vital Signs

Vital signs will be summarized for each treatment group using descriptive statistics at each scheduled assessment.

Electrocardiogram

RR, PR, QRS, QT, and QTc intervals will be summarized by treatment group at each scheduled assessment. Frequency tables for maximal QTc and maximal change in QTc at post-dose period using the categories suggested in the ICH E14 guidelines will be provided by treatment group.

Concomitant Medications

Concomitant medications of interest will be summarized for each treatment group.

Anti-evolocumab antibodies

The incidence and percentages of subjects who develop anti-AMG145 antibodies (binding and neutralizing) at anytime will be tabulated.

11. **REGULATORY OBLIGATIONS**

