4.1.5 Safety Endpoints

- Subject incidence of treatment-emergent adverse events
- Safety laboratory values and vital signs at each scheduled assessment
- ECG parameters (such as RR, PR, QRS, QT and QTc intervals) at each scheduled assessment
- Incidence of anti-evolocumab antibody (binding and neutralizing) formation

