10.7 Pharmacokinetic Analysis

Individual and mean serum evolocumab and PCSK9 concentration graphs will be provided by nominal time. The data set will be analyzed and stored in the Pharsight Knowledgebase Server (PKS) data repository using the current version of Phoenix WinNonlin. Evolocumab or PCSK9 serum concentrations with values below the lower limit of quantification will be reported as less than their respective values but will be set to zero for analysis. PK parameters following the last dose will include but not limited to the maximum and minimum evolocumab serum concentrations observed at the collected time points. Individual and summary statistics for PK concentrations will be provided.

These analyses will be performed by the CPMS group.

Compartmental exposure-response analyses will not be specified in this analysis plan but may be included in a subsequent population PK analysis using a single study or as part of a metadata analysis.

11. Changes From Protocol-specified Analyses

There are no changes to the protocol-specified analyses.

12. Literature Citations / References

Hochberg Y. A sharper Bonferroni procedure for multiple tests of significance. Biometrika 1988;75:800-802.

Littell, R.M., Pendergast, J and Natarajan, R. Tutorial in Biostatistics. Modelling covariance structure in the analysis of repeated measures data. Stat Med. 2000;19: 1793-1819.

Wiens BL. A fixed sequence Bonferroni procedure for testing multiple endpoints. *Pharmaceut Statist.* 2003;2:211–215.

The Task Force for the management of dyslipidaemias of the European Society of Cardiology (ESC) and the European Atherosclerosis Society (EAS). ESC/EAS Guidelines for the management of dyslipidaemias. *European Heart Journal.* 2011; 32:1769–1818.

13. Appendices

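### SAP 10.6.4 drops ECG observations with listed rhythm or conduction findings whether pre-existing or new on treatment, and no planned ECG output counts the new cases by arm

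*SAP*

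**What the plan says.** SAP 4.1.5 lists as a safety endpoint "ECG parameters (such as RR, PR, QRS, QT and QTc intervals) at each scheduled assessment". Protocol 10.5.3 plans the matching analysis: "RR, PR, QRS, QT, and QTc intervals will be summarized by treatment group at each scheduled assessment". It adds frequency tables for maximal QTc and maximal QTc change. Neither place mentions an exclusion by diagnosis.

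The exclusion appears in SAP 10.6.4. The section opens with on-treatment data: "For post-baseline assessments where ECG is performed in triplicate, the average of the 3 (or all available) readings will be used for analysis". The next sentence is the rule: "Observations with the following diagnosis or findings will be excluded from analysis: artificial pacemaker, atrial fibrillation, atrial flutter, left bundle branch block", with right bundle branch block as the last item. The outputs, reported visit by visit, follow: "PR, QRS, QT, QTc (i.e., QTcB and QTcF) and RR intervals and their change from baseline will be summarized for each treatment group by scheduled". For the categories, "subjects will be categorized and summarized per their maximum post-baseline absolute QTc interval using limits of 450 ms, 480 ms, and 500 ms", and maximum change is cut at 30 and 60 ms.

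SAP Section 11 states: "There are no changes to the protocol-specified analyses".

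**The concern.** A safety summary should not depend on the absence of the finding that it might reveal. Bundle branch block is a QRS finding, and atrial fibrillation is a rhythm finding that bears on RR. If a subject starts with a normal tracing and develops one of these on treatment, the rule removes that tracing from the outputs where it belongs. It treats a subject who entered with the same finding in exactly the same way. A reader of the ECG tables could not tell an expected exclusion from an emergent one, or see whether exclusions were balanced between evolocumab and placebo.

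The numbers at stake are small. In a 12-week safety assessment, though, a few uncounted subjects in one arm are what a categorical ECG table exists to show.

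**Working it through.** There is no stated figure to reproduce, so the check compares the sections and then sizes the loss on stated assumptions.

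**1. Scope of the rule (SAP 10.6.4).**
- Unit: observations, not subjects.
- Timing: nothing limits it to findings present at baseline, and the sentence before it concerns post-baseline triplicates.
- Intervals: nothing limits it to QT/QTc; the outputs that follow are PR, QRS, QT, QTcB, QTcF and RR.

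**2. What happens to individual subjects.** Protocol Table 1 schedules post-baseline ECGs at weeks 10 and 12 only.

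| Subject | Effect of the rule |
|---|---|
| Normal Day 1, new left bundle branch block at both visits | No scheduled post-baseline value left; out of the QRS summaries and both QTc categorizations |
| Normal Day 1, new atrial fibrillation at week 10 only | Week 10 lost; week 12 still contributes |
| Left bundle branch block on Day 1 and afterwards | On-treatment tracings dropped just as for a new case |
| QRS widening short of bundle branch block | Stays in |
| QTc or PR prolongation without a listed finding | Stays in |

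The third row can occur. Protocol exclusion criterion 203 bars uncontrolled arrhythmia in the 6 months before randomization, so controlled atrial fibrillation may enter, and no criterion names bundle branch block.

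**3. Whether another output replaces what is lost.**
- SAP 10.6.4 plans no count of excluded observations and no table of rhythm or conduction findings. By contrast, SAP 10.6.2 plans worst-shift tables for laboratory data and incidence counts for CK and liver tests.
- SAP 10.6.1 tabulates adverse events by preferred term, so a reported case appears there. Under Protocol 7.7.4, central cardiologists interpret all tracings, but the investigator's reading need not be reconciled with theirs. An asymptomatic finding on the central read may never be recorded as an event.
- SAP 10.6.3 summarizes heart rate without this exclusion, but heart rate identifies neither rhythm nor conduction.

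**4. Ambiguity.** SAP 10.6.4 does not say whether an observation is one reading or the whole triplicate. If one of three readings shows atrial fibrillation, a programmer could average the other two or drop all three. Nor does it say whether the rule applies to the Day 1 average that SAP 6.2 defines as baseline.

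**5. Size.** Arm sizes are the planned 300 (evolocumab) and 150 (placebo) from SAP 3.2. Three inputs are assumptions not found in the documents: a rate of new findings of 0.5% to 3% on evolocumab, 0.5% on placebo, and a 40 ms QRS increase per case. The last treats every case as a bundle branch block; a case of atrial fibrillation without block would add less to QRS.

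- Expected cases = n × rate. Placebo: 150 × 0.005 = 0.75.
- Chance of at least one evolocumab case = 1 − (1 − rate)^300.
- Shift in the mean QRS difference if cases were kept = 40 ms × (evolocumab rate − placebo rate).

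| Evolocumab rate | Expected cases of 300 | Chance of at least one | QRS mean shift |
|---|---|---|---|
| 0.5% | 1.5 | 0.778 | 0.0 ms |
| 1% | 3.0 | 0.951 | 0.2 ms |
| 2% | 6.0 | 0.998 | 0.6 ms |
| 3% | 9.0 | 1.000 | 1.0 ms |

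At the 3% rate the ECG tables would omit a 9 against 0.75 split in expected cases, while the mean would have moved by only 1 ms.

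**The case against.** The case for leaving the plan alone has several parts.

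*The exclusion is sound for QT/QTc.* With bundle branch block or pacing, QTc partly reflects the wide QRS, and PR is undefined in atrial fibrillation. This stands, and it is why new-onset cases should not simply be put back into the main QTc categories. It does not justify dropping QRS and RR or leaving the exclusions uncounted.

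*Detection happens elsewhere.* The site receives a cardiologist-reviewed report that the investigator must initial and date. The allowance for not recording clinically insignificant abnormalities is written for laboratory findings, not ECGs. Adverse events are tabulated, heart rate is summarized, and the data monitoring committee reviews accumulating data. This stands in part: clinically recognized cases should surface. What remains is the finding seen centrally but not recorded as an event.

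*The endpoint is interval parameters, and no diagnosis table was promised.* True. But QRS and RR are named parameters, and the rule selects among their values by diagnosis.

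*SAP Section 11 need not list a data-handling detail on which the protocol is silent.* This largely stands. Noting the rule there is a matter of transparency, not the correction of a contradiction.

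A reader might go further and infer that the ECG outputs cannot show any treatment-emergent conduction or rhythm change, or that the arms would look alike whatever happened. The documents do not support that. Only the listed diagnoses are removed. A subject affected at one visit still contributes the other, and all remaining interval changes stay in the tables.

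**Conclusion.** The point holds for the listed diagnoses. As written, SAP 10.6.4 removes new on-treatment atrial fibrillation or flutter, left or right bundle branch block, and paced rhythm from the QRS and RR summaries and the QTc categories, and no planned ECG output counts those cases by arm. The adverse event tables are a partial backstop.

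The effect on mean summaries is likely small. The loss is in the count of new findings and in the affected subjects' category entries: 1.5 to 9 subjects per 300-subject evolocumab arm at the assumed rates. The reading of the rule rests on the text alone, but its size rests on assumed rates, because the documents give none. It has no bearing on the efficacy conclusions. The change is worth making because it removes outcome-dependent selection from a safety endpoint at little cost.

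**What to change.** In SAP 10.6.4:

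1. Limit the exclusion to QT/QTc, and to PR where it cannot be measured. Keep QRS and RR observations.
2. If wanted, keep excluded tracings out of the main QTc categories. Report by arm and visit how many observations and subjects were excluded, split into present at baseline and new onset, and list the QTc values of new-onset cases separately.
3. Add a table by treatment group of the listed findings, baseline against worst post-baseline, from the central ECG interpretation.
4. State whether an observation is a single reading or the triplicate, and whether the rule applies to the baseline value in SAP 6.2.

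Note the exclusion in SAP Section 11.

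The cost is SAP wording, one or two more tables from data already collected, and slightly more spread in the QRS and RR summaries.

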10.6.5 Antibody Formation

The incidence and percentage of subjects who develop anti-evolocumab antibodies (binding and if positive, neutralizing) at anytime will be tabulated.

10.6.6 Exposure to Investigational Product

Descriptive statistics will be produced to describe the patient-month exposure to investigational product and the categorical representation of dose received.

Exposure definitions are provided in Section 6.3.

Descriptive statistics will be produced to describe the patient-month exposure to atorvastatin background therapy and the total quantity of atorvastatin used by treatment group.

10.6.8 Exposure to Concomitant Medication

The number and proportion of subjects receiving the lipid regulating medications of interest (MOI) will be summarized by category and preferred term for each treatment group as coded by the World Health Organization Drug (WHO Drug) dictionary.

10.7 Pharmacokinetic Analysis

Individual and mean serum evolocumab and PCSK9 concentration graphs will be provided by nominal time. The data set will be analyzed and stored in the Pharsight Knowledgebase Server (PKS) data repository using the current version of Phoenix WinNonlin. Evolocumab or PCSK9 serum concentrations with values below the lower limit of quantification will be reported as less than their respective values but will be set to zero for analysis. PK parameters following the last dose will include but not limited to the maximum and minimum evolocumab serum concentrations observed at the collected time points. Individual and summary statistics for PK concentrations will be provided.

These analyses will be performed by the CPMS group.

Compartmental exposure-response analyses will not be specified in this analysis plan but may be included in a subsequent population PK analysis using a single study or as part of a metadata analysis.

11. Changes From Protocol-specified Analyses

There are no changes to the protocol-specified analyses.

12. Literature Citations / References

Hochberg Y. A sharper Bonferroni procedure for multiple tests of significance. Biometrika 1988;75:800-802.

Littell, R.M., Pendergast, J and Natarajan, R. Tutorial in Biostatistics. Modelling covariance structure in the analysis of repeated measures data. Stat Med. 2000;19: 1793-1819.

Wiens BL. A fixed sequence Bonferroni procedure for testing multiple endpoints. *Pharmaceut Statist.* 2003;2:211–215.

The Task Force for the management of dyslipidaemias of the European Society of Cardiology (ESC) and the European Atherosclerosis Society (EAS). ESC/EAS Guidelines for the management of dyslipidaemias. *European Heart Journal.* 2011; 32:1769–1818.

13. Appendices

Appendix A. Analytical Study Week/Time Point Assignments

Selected endpoints will be summarized by scheduled study visits in descriptive analyses. Since the actual visits may not exactly coincide with their scheduled visit day, the actual visit day is mapped to the study visit generally by non-overlapping consecutive intervals covering the entire time continuum. The mapping intervals for all distinct schedules are summarized in the following table:

	Week	Week	Week	Week
Analytical Study Week	2	8	10	12
Scheduled Visit Day	15	57	71	85
Lipids, PK, PCSK9	(1, 35]	(35, 63]	(63, 77]	(77, 91]
Vital Signs	(1, 42]		(42, 77]	(77, 91]
Lp(a), ApoA1, ApoB100			(1, 77]	(77, 91]
Chemistry, Hematology		(1, 70]		>70
12 lead ECG			(1, 77]	>77
Body Weight, Waist Circumference, hsCRP, HbA1c, MMTT , Anti-evolocumab Antibodies, Urinalysis				> 1

Handling multiple records assigned to an analytical study week:

If there is more than one record in a study week interval, the analytical record for that specific study week will be defined as the record closest to the scheduled visit day of that specific study week (7 x study week + 1). If two records are equidistant from the scheduled day, then the earlier record will be chosen. If there are multiple records on the same day, the last record will be used.

Appendix B. Common Terminology Criteria for AEs (CTCAE)

Refer to the NCI Common Terminology Criteria for Adverse Events (CTCAE) for adverse event grading and information. The CTCAE is available at the following link: http://evs.nci.nih.gov/ftp1/CTCAE/About.html

(Group A) Intensive statin usage	 Subject has at least one of the following recorded for the last 4 weeks prior to screening: atorvastatin ≥ 40 mg QD rosuvastatin ≥ 20 mg QD simvastatin ≥ 80 mg QD (note that simvastatin 80 mg QD is not approved in some countries, e.g., the United States) any statin¹ QD plus ezetimibe 	
(Group B) Non-intensive statin usage	Subject has been taking any dose of a statin at least weekly for the last 4 weeks prior to screening and is not included in Group A	
(Group C) No statin	Subject is not included in Group A or Group B	

Annendiy C	Linid Modify	ving Background	I Therapy Intensity
Appendix C.		ing Dackyround	п петару пцепъцу

Note:

¹ Statin includes atorvastatin, fluvastatin, lovastatin, pitavastatin, pravastatin, rosuvastatin, and simvastatin.
